5.6	Variables to be Measured to Demonstrate Achievement of Endpoints	18
5.7	Measures to be Taken to Avoid or Minimize Bias	18
6	Statistical Considerations	18
6.1	Hypotheses to be Tested.....	18
6.1.1	Hypothesis to be Tested in Patients with Attempted Endoscopic Stent Retrieval	18
6.1.2	Hypothesis to be Tested in Patients with Benign Indications.....	19
6.2	Sample Size	19
6.3	Missing Data.....	20
6.4	Site-level Poolability	20
6.5	General Analysis.....	21
6.6	Limitations of the Investigation.....	22
7	Methods.....	22
7.1	Subject Consent	22

7.2	Medications.....	22
7.3	Stent Placement Procedure	22
7.4	Point of Enrollment.....	23
7.5	Post-stent Placement Procedure and Discharge.....	23
7.6	Follow-up Post-stent Placement	24
7.7	Stent Repositioning.....	26
7.8	Stent Removal.....	26
7.9	Duration of Study and Subject Participation	27
7.10	Study Exit	27
7.11	Criteria and Procedures for Withdrawal	28
8	Deviations from Clinical Investigation Plan	28
9	Data Collection and Reporting	28
9.1	Electronic Case Report Forms (eCRF system)	28
9.2	Data Reporting.....	29
10	Data Management and Quality Assurance	29
10.1	Data Entry and Quality Assurance	29
10.2	Data Monitoring Arrangements	29
11	Safety Monitoring and Procedures for Reporting Adverse Events	29
11.1	Safety Monitoring.....	29
11.2	Adverse Event Reporting.....	30
12	Early Termination or Suspension of the Investigation	30
13	Ethical Considerations.....	30
14	Publication Policy.....	30
15	Trial Administration and Investigators.....	30
15.1	Approvals and Agreements.....	31
15.2	Investigators.....	31
15.3	Insurance.....	31

Appendices

Contact Information.....	Appendix A
Written Procedures for Monitoring Clinical Investigations	Appendix B
Definitions	Appendix C

1 Clinical Investigation Plan Overview

This prospective, multicenter, single-arm clinical investigation will evaluate the endoscopic removability of the Evolution® Esophageal fully covered stent. Patients may be enrolled in the study when a patient requires stenting for an obstruction caused by an intrinsic or extrinsic malignancy; refractory benign esophageal stricture; or to seal an esophageal fistula, perforation, or leak. Patients will be enrolled at up to 15 investigative sites until a maximum of 130 patients have been enrolled to ensure that 58 patients have had endoscopic stent removal attempted after an indwell time of at least 7 days, but no more than 6 months.

Figure 1 presents a flow diagram of the study design.

[figure not shown]

Figure 1. Study flow diagram.

2 Objectives of the Clinical Investigation

2.1 Primary Objective

The primary objective of this study is to evaluate the endoscopic removability of the stent component of the Evolution® Esophageal Stent System – Fully Covered (known as the Evolution® Esophageal fully covered stent) when used to treat patients with an obstruction caused by an intrinsic or extrinsic malignancy; refractory benign esophageal strictures; or esophageal fistulas, perforations, or leaks.

The **primary endpoint** will be the proportion of patients, of those patients in whom endoscopic retrieval is attempted after an indwell time of between 7 days and 6 months, who have successful stent removal (see Appendix C) of the Evolution® Esophageal fully covered stent. [REDACTED]

2.2 Additional Objectives

Other objectives for the study are to collect and evaluate additional outcome measures, including effectiveness of the stent in benign conditions, as outlined in section 5.5 Endpoints.

3 Product Description and Intended Use

3.1 General Product Description

The Evolution® Esophageal fully covered stent is a flexible, self-expanding stent constructed of a single, woven, nitinol wire (**Figure 2**). Due to its design, the stent foreshortens as it expands. It is fully covered. [REDACTED]

[REDACTED] To aid in visibility under fluoroscopy, there are four radiopaque marker bands at either end of the stent. The stent has lassos, which include grasping features, at the proximal and distal ends of the stent that are used in stent repositioning and stent removal. The total length of the stent is indicated by radiopaque markers on the inner catheter of the delivery system; the radiopaque markers indicate the actual stent length when expanded to nominal stent diameter.

Figure 2. Photograph of the Evolution® Esophageal fully covered stent. 1= Lasso loop grasping feature, 2 = Crown, and 3 = Radiopaque marker band

The stent is mounted on an inner catheter, which accepts a 0.035 inch wire guide, and is constrained by an outer catheter. A pistol-grip delivery handle allows stent deployment or recapture (**Figure 3**).

Figure 3. Delivery system handle

3.2 Intended Use

The Cook Evolution[®] Esophageal Stent System – Fully Covered is indicated in this study to maintain luminal patency of the esophagus in cases of obstruction caused by intrinsic or extrinsic malignancies; refractory benign strictures; or to seal esophageal fistulas, leaks, and perforations.

3.3 Product Identification and Tracking

The Evolution[®] Esophageal Stent System – Fully Covered will be tracked throughout the course of the study by means of a Product Log that includes information such as serial numbers, quantity, and disposition of product. A Product Log will be maintained by each investigative site. In addition, information such as the size and lot number of products used in each patient will be recorded on individual case report forms.

The device is available in several diameters and length options as detailed in Table 1.

Table 1. Evolution[®] Esophageal fully covered stent dimensions

RPN	Body (mm)	Flange (mm)	Length (cm)
EVO-FC-R-18-23-8-E-CI	18	23	8
EVO-FC-R-18-23-10-E-CI	18	23	10
EVO-FC-R-18-23-12-E-CI	18	23	12
EVO-FC-R-20-25-8-E-CI	20	25	8
EVO-FC-R-20-25-10-E-CI	20	25	10
EVO-FC-R-20-25-12-E-CI	20	25	12

3.4 Instructions for Use

Refer to the manufacturer's Instructions for Use (IFU) for the following:

[figure not shown]
[figure not shown]

- Complete instructions including storage and handling requirements, preparation for use, pre-use checks, and precautions to be taken during use, after use and disposal
- Complete summary of the necessary training and experience required for use of these devices
- Complete description of the procedures involved in the use of these devices
- Contraindications, relative contraindications, and warnings for the devices

4 Risk Analysis and Risk Assessment

4.1 Risks and Foreseeable Adverse Events

As part of the stent implantation and removal, endoscopic procedures may also need to be performed. These procedures are generally recognized as safe, although risks have been noted with these procedures. Potential risks associated with endoscopic procedures and/or esophageal stenting and removal include, but are not limited to:

- Perforation
- Hemorrhage
- Aspiration, reflux, vomiting
- Fever, infection
- Allergic reaction (e.g., to medication)
- Hypotension
- Respiratory compromise, depression, or arrest
- Cardiac arrhythmia or arrest
- Stent misplacement and/or migration
- Tumor and tissue ingrowth and overgrowth, 
-  
- Dysphagia 
- Esophageal ulceration and erosion
- Tear/tissue damage 
- Wire entrapment
- Nausea
- Pain
- Foreign body sensation or reaction
- Esophagitis

- Edema
- Food bolus impaction
- Gas bloat syndrome
- Sensitivity to device components
- Fistula (e.g., involving trachea, bronchi, or pleural space)
- Intestinal obstruction secondary to migration
- Mediastinitis or peritonitis
- Airway compression
- Tracheal obstruction
- Compression of adjacent structures
- Death (other than due to normal disease progression)

It is also important to note that the decision to remove or reposition the stent is based on the physician's clinical judgment. Pre-existing conditions (e.g., stricture, fistula, perforation, leak) may not be healed at the time of stent removal and may require additional intervention.

4.2 Methods to Minimize Risks

This device will be used only by trained gastroenterologists who are experienced in endoscopic procedures. Physicians who may remove the stent endoscopically will be trained on the removal procedure. Patients will be selected according to this study's labeled indication and in accordance with the inclusion/exclusion criteria outlined in this document. There are no

restrictions on the use of medications or other standard of care procedures used to maintain patient comfort and speed recovery peri-procedurally.

5 Design of the Clinical Investigation

5.1 Type of Investigation

This prospective, multicenter, single-arm clinical investigation will evaluate the endoscopic removability of the Evolution® Esophageal fully covered stent in patients with esophageal obstruction caused by intrinsic or extrinsic malignancies; refractory benign esophageal strictures; or esophageal fistulas, perforations, or leaks.

Patients will be enrolled at up to 15 investigative sites until a maximum of 130 patients have been enrolled to ensure that 58 patients have had endoscopic stent removal attempted after an indwell time of at least 7 days, but no more than 6 months. A patient can be enrolled in the study when the patient requires stenting for an obstruction caused by an intrinsic or extrinsic malignancy; refractory benign esophageal stricture; or to seal an esophageal fistula, perforation, or leak.

Enrollment is expected to be completed within 24 months of initiating the study.

Figure 1 (page 8) presents a flow diagram of the study design.

5.2 Inclusion Criteria

Patient enrollment shall be based on known information at the time of procedure. It will not be considered a violation of the clinical investigation plan (CIP) if information obtained at a later date contradicts information collected at the time of procedure.

Patient may be included if one of the following is met:

- Diagnosed with a benign esophageal stricture [REDACTED]
[REDACTED]
[REDACTED]
- Diagnosed with a malignant intrinsic or extrinsic esophageal obstruction (e.g., stricture)
[REDACTED]
[REDACTED]
- Diagnosed with a benign esophageal fistula, perforation, or leak [REDACTED]
[REDACTED]
[REDACTED]
- Diagnosed with a malignant esophageal fistula, perforation, or leak [REDACTED]
[REDACTED]

Note: Physicians will use their best estimate regarding expected time frames for endoscopic stent removal or stent replacement when considering a patient for inclusion in the study. [REDACTED]

5.3 General Exclusion Criteria

Patient will be excluded if any of the following are met:

- Patient is < 18 years of age
 - Patient is unable or unwilling to provide written informed consent
 - Patient is unable or unwilling to comply with the follow-up schedule
 - Patient is pregnant, lactating, or planning on being pregnant within the next 6 months
 - Patient is simultaneously participating in another investigational drug or device study
- [REDACTED]

- [REDACTED]
- Patient that is contraindicated to upper GI endoscopy and/or any procedure to be performed in conjunction with esophageal stent placement (e.g., patients in whom endoscopy procedures cannot safely be performed)
 - Patient has a medical condition or disorder that would limit life expectancy to less than the primary study endpoint or that may cause noncompliance with the protocol or confound the data analysis
 - Patient has a known hypersensitivity or contraindication to study products that, in the opinion of the investigator, cannot be adequately pre-medicated [REDACTED]
 - Patient is not a candidate for tumor reduction therapy or surgical resection
Note: This criterion applies only to patients diagnosed with a malignant intrinsic or extrinsic esophageal obstruction, or with a malignant esophageal fistula, perforation, or leak.

5.4 Endoscopically-confirmed Exclusion Criteria

[REDACTED]

5.5 Endpoints

5.5.1 Primary Endpoint

Since the objective of the study is to evaluate endoscopic removability of the stent when used as intended, the **primary endpoint** will be the proportion of patients, in whom retrieval is attempted endoscopically after an indwell time between 7 days and 6 months, who have successful removal (see Appendix C) of the Evolution® Esophageal fully covered stent.

[REDACTED]

[REDACTED]

5.5.2 Secondary Endpoints

Secondary endpoints will include:

[REDACTED]

- **Clinical success**
 - In patients with strictures: improvement or relief of dysphagia symptoms (Appendix C) at the 7-day post-stent follow-up
 - In patients with fistulas, perforations, or leaks: seal sufficient to enable oral intake at the 7-day post-stent follow-up

[REDACTED]

These endpoints were chosen to supplement the primary endpoint. [REDACTED]

[REDACTED]

5.6 Variables to be Measured to Demonstrate Achievement of Endpoints

The primary endpoint will evaluate endoscopic removability of the Evolution® Esophageal fully covered stent. Specifically, the ability to completely remove the stent, incidence of tissue damage requiring immediate intervention, and hemorrhage requiring immediate intervention will be collected. Information regarding adverse events will be collected throughout this study during clinical assessments or telephone contact with the patients.

The clinical data will be collected on standardized case report forms. The schedule for assessments is summarized in Table 2 (section 7.6).

5.7 Measures to be Taken to Avoid or Minimize Bias

This study is not randomized or blinded. It is intended to prospectively collect information regarding the endoscopic removability of the Evolution® Esophageal fully covered stent.

6 Statistical Considerations

6.1 Hypotheses to be Tested

6.1.1 Hypothesis to be Tested in Patients with Attempted Endoscopic Stent Retrieval

Null

Hypothesis: The percentage of patients, in whom endoscopic retrieval is attempted after an indwell time of at least 7 days, but no more than 6 months, who have successful removal of the Evolution® Esophageal fully covered stent is less than or equal to the performance goal of 88%.

$$H_0: \gamma \leq 88\%$$

Alternative

Hypothesis: The percentage of patients, in whom endoscopic retrieval is attempted after an indwell time of at least 7 days, but no more than 6 months, who have successful removal of the Evolution® Esophageal fully covered stent is greater than the performance goal of 88%.

$$H_a: \gamma > 88\%$$

6.1.2 Hypothesis to be Tested in Patients with Benign Indications

Null

Hypothesis: The rate of clinical success in patients with benign indications is less than or equal to the performance goal of 80%.

$$H_{2_0}: \pi \leq 80\%$$

Alternative

Hypothesis: The rate of clinical success in patients with benign indications is greater than the performance goal of 80%.

$$H_{2_a}: \pi > 80\%$$

6.2 Sample Size

The study is designed to enroll a maximum of 130 patients to ensure that 58 patients have had an attempted endoscopic stent removal after an indwell time of at least 7 days, but no more than 6 months, to evaluate the primary hypothesis (section 6.1). Patients may be enrolled at up to 15 investigative sites, with no requirements regarding the maximum or minimum number of patients able to be enrolled at any given site.

[REDACTED]

[REDACTED]

Cook intends to enroll a maximum of 130 patients to ensure that 58 patients have

had an attempted endoscopic stent removal after an indwell time of at least 7 days, but no more than 6 months.

[REDACTED]

6.3 Missing Data

[REDACTED]

Appropriate summary statistics will be presented for the 58 patient cohort, as well as all the enrolled patients when appropriate, based on available data. Patient withdrawals and lost to follow-up will be tabulated and assessed for their potential impact on the study results. Specifically, if any patients withdraw or become lost to follow-up prior to the analysis of the 58 patients with stent removal, then the primary endpoint will be examined for the sensitivity of the results on these missing data via tipping point analysis.

[REDACTED]

6.4 Site-level Poolability

At the final analysis, poolability of data from multiple sites will be verified by examining the primary and secondary endpoints among sites as well as important patient baseline characteristics. Site-level poolability will be considered appropriate provided that these measures are similar among sites.

It is expected that some sites may have too few patients to provide reasonable site-level estimates of primary, secondary, and baseline measures. Pooling of this information will be explored based on hospital size (large versus small), site enrollment (large versus small), type of hospital (community versus teaching), and other group-wise strategies.

It is recognized that patient baseline characteristics may differ among sites, with some sites routinely treating patients with more severe disease progression. It is anticipated that the primary and secondary endpoint measures may be related to covariates that reflect this disease

progression, which are in turn related to outcome. Thus, observed site-specific differences among the primary or secondary endpoints will be checked for confounding with other measured covariates (e.g., age, sex). This can be accomplished using regression models (linear and logistic where appropriate) that include site and other measured covariates as independent variables.

Should one or more sites be found to differ significantly from the rest, then subsequent analyses may include the discriminating covariate or a covariate to distinguish between the unusual site(s) and those sites that are considered poolable.

6.5 General Analysis

The first 58 patients with attempted endoscopic stent removal (see Appendix C for definition) after an indwell time of at least 7 days, but no more than 6 months, will be included [REDACTED]. It is recognized that additional patients enrolled prior to the 58th attempted endoscopic stent removal may also have stent removal attempted prior to exiting the study. Those additional patients will be followed until reaching a study endpoint; however, these patients will not be initially included [REDACTED]

Secondary endpoints may be analyzed separately and/or together for those patients with attempted stent removal compared to those patients without attempted stent removal. [REDACTED]

Descriptive summaries will be provided where appropriate for each of the primary and secondary variables. In general, summaries will be complete over the total population. Continuous variable summaries will include the number of subjects (N), mean, standard deviation, minimum, and maximum. Categorical variable summaries will include the frequency and percentage of subjects who are in the particular category. In general, the denominator for the percentage calculation will be based upon the total number of subjects with the measurement for the total population and by treatment group, unless otherwise specified.

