7.4 Point of Enrollment

Point of enrollment will be based on the intent-to-treat population, and is defined to include any patient for whom the treatment procedure is initiated. More specifically, once the delivery system of the study device (Evolution® Esophageal Stent System – Fully Covered) has been inserted into the patient, this patient would be included in the intent-to-treat population. Cook intends to enroll a maximum of 130 patients to ensure that 58 patients have had endoscopic stent removal attempted after an indwell time of at least 7 days, but no more than 6 months. The first 58 patients with attempted endoscopic stent removal after an indwell time of at least 7 days, but no more than 6 months, will be included [REDACTED]. Additional analyses on remaining endpoints may be performed on all enrolled patients, as applicable, including an analysis on clinical success of the stent in benign conditions.

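### Does taking the first 58 removal attempts by date bias the primary success rate, and is a firm analysis of all in-window attempts needed?

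*Combined protocol and SAP*

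**What the plan says.** Section 6.1.1 tests whether the success rate exceeds 88% among patients with an endoscopic removal attempt at 7 days to 6 months of indwell. Section 6.2 caps enrolment at 130 so as to obtain 58 such patients.

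Section 6.5 names the cohort: "The first 58 patients with attempted endoscopic stent removal (see Appendix C for definition) after an indwell time of at least 7 days". Section 7.4 gives the same rule: "The first 58 patients with attempted endoscopic stent removal after an indwell time of at least 7 days, but no more than 6 months". Section 6.5 then shows that the order is by attempt, because it recognises that "additional patients enrolled prior to the 58th attempted endoscopic stent removal may also have stent removal attempted prior to exiting the study". It continues: "Those additional patients will be followed until reaching a study endpoint; however, these patients will not be initially included". The rest of that sentence is redacted.

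Three visible statements reach beyond the 58:

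- Section 6.5: "Descriptive summaries will be provided where appropriate for each of the primary and secondary variables", and "In general, summaries will be complete over the total population". Percentages generally use the subjects with the measurement as denominator.
- Section 6.3: "Appropriate summary statistics will be presented for the 58 patient cohort, as well as all the enrolled patients when appropriate, based on available data".
- Section 7.4: "Additional analyses on remaining endpoints may be performed on all enrolled patients, as applicable".

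**The concern.** The hypothesis covers the whole window from 7 days to 6 months, but a cut-off at the 58th attempt does not sample that window evenly. Among patients enrolled shortly before the cut-off, those with short indwell are counted and those with long indwell are not. If long-dwelling stents are harder to remove cleanly, the first 58 would give a slightly favourable rate.

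The wording on wider analyses is also soft. Summaries are given where or when appropriate, section 7.4 speaks of remaining endpoints that may be analysed, and nothing visible is broken down by indwell time. The tipping-point analysis in section 6.3 deals with withdrawals and losses, not with attempts made after the 58th. A reader could therefore fear that the most informative long-indwell removals would never be set beside the primary result.

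**Working it through.** **Inputs from the documents.** Target 58 attempts, maximum 130 enrolled (6.2), so 58/130 = 44.6% is the lowest attempt share that yields 58. Enrolment is expected within 24 months (5.1). The window is 7 days to 6 months and the performance goal 88% (6.1.1). Section 7.8 says that indwell may differ by indication but gives no distribution. The visible text gives no attempt share and no success rate by indwell.

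**The plan's own figure.** The inputs behind 58 are redacted, so it cannot be derived. It fits plausible ones: an exact binomial test against 88% at one-sided 0.025 needs 58 for 80% power at a true rate of 97.5%. Success then requires at least 56/58, with exact type I error 0.024.

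**Assumptions.** Random (Poisson) accrual of up to 130 patients over 24 months; indwell uniform on 7 to 180 days; enrolment stops at the 58th attempt; attempt share 44.6%, 60% or 80%; success falling linearly from 0.99 at day 7 to 0.80 at day 180. The comparison group is all in-window attempts among patients enrolled by the 58th attempt. There were 6,000 simulated trials per scenario.

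| Attempt share | Trials reaching 58 | Attempts outside the 58 | Mean indwell, 58 vs all (days) | Difference (days) | Bias (points) |
|---|---|---|---|---|---|
| 44.6% | 54% | 3.7 | 91.2 vs 93.6 | 2.3 | +0.26 |
| 60% | 100% | 9.9 | 88.8 vs 93.4 | 4.6 | +0.50 |
| 80% | 100% | 13.2 | 87.4 vs 93.5 | 6.0 | +0.66 |

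The 44.6% row averages only the trials that reach 58. In the other 46% nothing is left out. Over all trials that row becomes 2.0 attempts, about 1.3 days and +0.14 points.

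**Check by hand.** The assumed slope is 19 points / 173 days = 0.110 points per day. Bias = slope × indwell difference: 0.110 × 2.3 = 0.25, 0.110 × 4.6 = 0.51, 0.110 × 6.0 = 0.66. These agree with the table to rounding. If success does not depend on indwell, the slope is 0 and so is the bias.

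**Scale.** The standard error at 90% success is √(0.9 × 0.1 / 58) = 0.039, or 3.9 points. The largest bias in the table is 0.66 / 3.9 = 0.17 of a standard error, or 0.0066 × 58 = 0.38 of one patient.

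**Sensitivity.**

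- Other indwell shapes at 24 months: early-skewed +0.20 to +0.44 points, late-skewed +0.17 to +0.45, bimodal +0.34 to +0.97.
- Faster accrual, uniform indwell: +0.30 to +0.89 points at 18 months, +0.37 to +1.33 at 12 months (low ends again conditional on reaching 58).
- A step instead of a line, with 97% success up to 90 days and 80% after, at 60% or 75% attempting: 0.7 to 0.9 points at 24 months, 1.3 to 1.7 at 12 months. The extreme, 0.017 × 58, is about one patient.

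**The wider analyses.** Section 6.5 applies descriptive summaries to the primary variable, generally over the total population, with subjects measured as the denominator. Read naturally, that is the success rate over all attempts. Section 6.3 places the 58 and all enrolled patients side by side. The later attempters are followed, so their data will exist.

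**The case for a change.** The best case for a change is that the attempts left out are not a random handful. In the 24-month simulations 75% to 88% of them exceed 90 days of indwell, against 52% of all attempts, so they say most about the later part of the window. The test is also coarse: against 88%, 55/58 gives one-sided p = 0.071 and 56/58 gives p = 0.024, so a single patient can decide it. A supportive analysis of all in-window attempts would cost little, because these patients are followed anyway.

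The direction of the lean stands, and so does the value of seeing the later removals. The need to amend the plan does not. A supportive analysis would leave the cohort, the 58, the test and its decision as they are, so the coarseness of the test is no argument for it. What it would add to the visible text is a firmer verb, an exact interval and a breakdown by indwell, all of which an analyst can supply when reporting the summaries already planned. It may also be in the plan already: the sentence is blacked out straight after saying that these patients are not initially included, which suggests later inclusion. Redacted text cannot be counted as missing.

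Ordering by enrolment would remove the lean (94.6 days against 94.5 for all attempts, with uniform indwell and 60% attempting). The price is waiting until every earlier enrollee has had an attempt or left the study. The present rule is prespecified and objective, and all 58 patients meet the eligibility window in the hypothesis, which sets no particular mix of indwell times.

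**Conclusion.** No change is called for. Sections 6.5 and 7.4 do order the 58 by attempt, and if more than 58 in-window attempts occur the cohort may lean to shorter indwell, by about 2 to 6 days in the mean at 24-month accrual with uniform indwell. The success rate is biased only if success falls with indwell. Under an assumed 19-point fall the bias is at most about 0.7 points with uniform indwell and just under 1 point with a bimodal shape, against a standard error of 3.9 points. Figures above 1 point need accrual much faster than the plan expects. The indwell distribution, attempt share and success-by-indwell relation are all assumptions.

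Followed as written, the plan gives a sound primary conclusion, and the visible summaries leave room to show the later attempts. At most, the sponsor could be asked to confirm that section 6.5 reports the primary endpoint for all in-window attempts, with indwell time, as a supportive result beside the first 58.

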7.6 Follow-up Post-stent Placement

Patients will be followed after stent placement according to the schedule below unless the stent is removed (surgically or endoscopically), a non-study stent is placed, or other study exit (e.g., death, withdrawal, lost to follow-up) has occurred:

Clinic visit	7 days (range 5-12 days)
Telephone	1 month \pm 7 days
	2 months \pm 7 days
	3 months \pm 7 days
	4 months \pm 7 days
	5 months \pm 7 days
	6 months \pm 7 days

If a patient completes a required visit outside of the prescribed follow-up window, it will be recorded as a deviation from the clinical investigation plan.

Patients enrolled in the study will be followed an additional 30 days following endoscopic stent removal, unless replaced with another non-study stent. If the study stent is surgically removed (e.g., during esophagectomy), the patient will immediately exit the study. If a non-study stent is placed (either before or after stent removal), the patient will immediately exit the study (note: overlapping stents is not recommended per the IFU). If the stent removal procedure occurs at the 6-month follow-up, patients will be followed an additional 30 days following the stent removal procedure. The data collection schedule is provided in Table 2.

For all telephone contacts, a prescribed script is recommended to collect the required data. At least three attempts to contact the patient should be made and documented in the study source documents. If the patient still cannot be reached it may be considered a missed visit/telephone contact. Of note, data may be collected at a clinic visit instead of a telephone call if preferred by the patient and/or physician.

Table 2. Data collection schedule

Data collection schedule ¹	Pre-procedure	Stent placement procedure/discharge	7-day ² (5-12 days)	1-month ² (23-37 days)	2-month ² (53-67 days)	3-month ² (83-97 days)	4-month ² (113-127 days)	5-month ² (143-157 days)	6-month ² (173-187 days)	Stent removal	30 days post-stent removal
Informed Consent	X										
Inclusion/Exclusion	X	X									
Medical History	X										
Lesion Characteristics		X									
Dysphagia Score	X		X	X	X	X	X	X	X	X	X
Endoscopy ²		X								X	
Radiographic Assessment ²		X ³								X ³	
Telephone Contact ⁴				X	X	X	X	X	X		X
Clinic Visit ⁴	X	X	X							X	

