7.9 Duration of Study and Subject Participation

Patient recruitment should be completed within 24 months of initiating the study. Follow-up data will continue to be collected for six months after stent deployment for each patient in the study, unless a patient exits the study as discussed below (reminder: the patient will be followed for an additional 30 days if the stent is removed at the 6-month follow-up).

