7.10 Study Exit

A patient will be considered to have exited the study when one of the following has occurred:

- Voluntary withdrawal
- Lost to follow-up
- Death
- 30 days post endoscopic stent removal
- Stent is surgically removed (e.g., during esophagectomy)
- Non-study stent is implanted (e.g., inside study stent or after study stent is removed)
- 6 months if the stent has not been removed or replaced

After a patient exits the study, the physician may continue to follow the patient per the institution's standard of care. No additional data will be submitted to the data coordinating center once a patient has exited the study.

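### Does capping the primary cohort at 6 months of indwell, while the 6-month contact window runs to day 187, distort the primary analysis?

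*Combined protocol and SAP*

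**What the plan says.** All passages are in the combined protocol and SAP.

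- **Cohort and endpoint.** Section 6.5 starts from "The first 58 patients with attempted endoscopic stent removal" and restricts them to attempts "after an indwell time of at least 7 days, but no more than 6 months". Section 5.5.1 defines the endpoint for attempts "after an indwell time between 7 days and 6 months". Sections 2.1, 6.1.1 and 6.2 carry the same range, and none of the visible text converts 6 months to days.
- **Contact schedule.** Table 2 in section 7.6 sets the 6-month contact at days 173-187. It is a telephone contact that may be replaced by a clinic visit. Stent removal has its own column, with no day window.
- **Late removal.** Section 7.6 states: "If the stent removal procedure occurs at the 6-month follow-up, patients will be followed an additional 30 days following the stent removal procedure". Section 7.9 repeats it as a reminder: "the patient will be followed for an additional 30 days if the stent is removed at the 6-month follow-up".
- **Study exit.** Section 7.10 lists "6 months if the stent has not been removed or replaced" among the exit events, again with no day count.
- **Test.** Section 6.1.1 sets a performance goal of 88%. The significance level, the power and the assumed removal rate are redacted.

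**The concern.** On its face the plan invites a removal at the 6-month follow-up, allows that follow-up until day 187, and then admits to the primary analysis only attempts at 6 months or less. A patient who attends on schedule and has the stent taken out on day 185 seems to be compliant under section 7.6 and ineligible under section 6.5.

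Two things would be at stake. First, the attempts at risk lie at the top of the indwell range that the study sets out to cover. Second, the trial is single-arm and unblinded, with a small cohort tested against a fixed goal. If nobody has said whether 6 months means 180 days, a calendar date or the visit with its window, the status of a late attempt could be settled once its result is known. An excluded attempt is replaced by the next qualifying one while the enrolment cap of 130 allows, so the cohort size would not reveal the choice.

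**Working it through.** **1. How much of the window lies beyond the cap.** Every monthly window in Table 2 is 30k ± 7 days for k = 1 to 6 (23-37, 53-67, up to 173-187), so the schedule's own 6 months is day 180. The last window holds 187 − 173 + 1 = 15 days.

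| Reading of 6 months | Contact days beyond the cap | Share of window |
|---|---|---|
| 180 days | 181-187 (7 days) | 7/15 = 47% |
| Calendar, shortest (181 days) | 182-187 (6 days) | 6/15 = 40% |
| Calendar, longest (184 days) | 185-187 (3 days) | 3/15 = 20% |
| The 6-month visit including its window | none | 0 |

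These are shares of permitted contact days, not of removals. Section 7.8 leaves the timing of removal to the physician. The documents give no count of attempts on days 181-187. As a pure illustration, suppose attempts were spread evenly by day. The 174 days from 7 to 180 would hold the 58 attempts, and the 7 days after them would hold 58 × 7/174 = 2.3. Clustering at the last visit would raise that figure; earlier clinically driven removal would lower it, possibly to zero.

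**2. What one late failure can do.** The test is one-sided against 88%. Its exact p-value is P(X ≥ x) with X ~ Binomial(n, 0.88).

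- 56/58: 0.0006 + 0.0048 + 0.0185 = 0.0239
- 55/58: 0.0239 + 0.0471 = 0.0710
- 56/59: 0.0654

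The pair 56/59 and 56/58 looks like the natural comparison, but 59 is never the denominator: section 6.5 fixes the cohort at the first 58 qualifying attempts. The right comparison keeps n = 58 and swaps one patient. Let f be the number of failures among the other 57. With the late failure counted there are f + 1 failures in 58. With it replaced by a success there are f. At an assumed one-sided level of 0.025 or 0.05 the test passes with up to 2 failures (p = 0.0239) and not with 3 (p = 0.0710). The conclusion therefore turns on the classification only when f = 2 exactly, the late attempt fails, its replacement succeeds, and the late attempt falls among the first 58.

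**3. Whether the passages conflict.** Two consistent readings are available.

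- *Strict throughout.* If 6 months is day 180 in section 6.5, it is also day 180 in section 7.10. A patient with the stent still in place has then exited, and section 7.10 sends no further data after exit. A removal on day 185 is outside the study, not an in-study removal that the analysis discards.
- *By visit throughout.* If 6 months means the 6-month follow-up, sections 7.6 and 7.9 keep the patient in the study, and the attempt counts.

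The loss appears only when section 6.5 is read strictly and section 7.6 generously. The visible text does not say which consistent reading applies. That is the whole of the gap.

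**The case for a change.** The strongest reply is that choosing between two readings is exactly what a plan should do in advance. Days 185-187 exceed 6 months on any literal day count, yet sections 7.6 and 7.9 treat removal at the 6-month follow-up as ordinary. With so few failures allowed, one classification could decide the trial, and a sentence would prevent that at no cost.

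Part of this stands. The limit is not stated in days in the visible text, and a failure on the boundary could matter. If many attempts came late and did markedly worse, their handling would show: with an assumed 97% success up to day 180 and 80% afterwards, late shares of 1%, 5% and 10% give overall rates of 96.8%, 96.2% and 95.3%. Power at 56/58 is then 0.72, 0.61 and 0.48, against 0.75 with late attempts left out.

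That calculation assumes the point in dispute. The documents list tissue ingrowth as a risk but do not relate the difficulty of removal to indwell time, so neither the size nor the direction of any bias is supported. Nor is leaving out attempts beyond 6 months a bias in the primary rate, because the hypothesis in section 6.1.1 concerns attempts within that limit. Finally, text is redacted after the primary endpoint, within section 6.5 and in section 7.8, and the flow diagram is not shown. A definition in days may already stand there.

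**Conclusion.** No change is called for. The mismatch between the cap and the contact window is genuine, but it amounts to an undefined term at one edge of the cohort. Applied literally, the cap gives a sound answer to the question the plan asks. Applied by visit, it loses nothing. Analysts can settle the day count from placement to first attempt before looking at results, and it would affect what may be zero or very few attempts.

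The size is bounded: 3 to 7 of 15 contact days on literal readings, and a changed conclusion only when the other 57 attempts contain exactly 2 failures. Moving the cap to day 187 and shifting the exit rule would alter the indwell range under test, which is open to debate and not a correction.

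This rests on an assumed one-sided level of 0.025 or 0.05, on an unknown and probably small number of late attempts, and on the visible text alone.
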